7.8 Alpha error correction through multiple analyses

(ICH E3; 9.7.1, 11.4.2.5. ICH E9; 2.2.5)

The type-I error for primary biomarker analysis is 10%. As we analyze the inhibition of three biomarkers as primary variable (cyclin D1, Ki67 and active caspase 3), the type I error was divided into 3,3% (<5%) for each analysis.

Prior to the completion of the study, an interim analysis with a cut-off dated 08-May-2018 will be performed in case the study was not completed up to that date. The results will be presented at the ASCO annual meeting 2018. In order to correct the alpha error associated with multiple primary analyses, it was considered that only statistically significant biomarker differences could be declared when the analysis showed p-values <3.3% in the interim and the final analyses for both analysis populations (full analysis set and per protocol set).

For secondary analyses (analysis of the difference and correlation between the levels of different biomarkers), multiple analyses were corrected through Benjamini-Hochberg's procedure "false Discovery rate (FDR)" of 10%. This procedure lists the analyses performed from lowest to highest p-value. A difference is considered statistically relevant in an analysis if the p-value obtained is equal or lower than the range assigned in that analysis, divided into the number of analyses and multiplying by 10%.

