5.4 Sample size calculation

(ICH E3; 9.7.2. ICH E9; 3.5)

The primary objective is to identify, in human tumor samples, biomarker changes associated with short exposure to AZD2281 as potential predictors of activity in Endometrial Carcinoma (EC). The primary endpoint is the difference between pre and post treatment immunostaining of cyclin D1, Ki67 and active caspase 3 on endometrial tumor tissue, after four weeks of treatment. Therefore, the primary analysis will be based on comparing pre and post treatment immunostaining on target biomarkers. The histological

score will be obtained by applying the following formula: $Hscore = 1x(\%light staining) + 2x(\%moderate staining) + 3x(\%strong staining)$. Although a preliminary power analysis has been performed, in agreement with the exploratory nature of phase 0 studies, the sample size has been limited to 36 patients (It is expected that each participating site includes an average of about 6-10 patients) for clinical and practical considerations, rather than statistical ones (Kummar et al 2009).

Analysis will be performed in accordance with a statistical evaluation scheme specifically developed for Phase 0 trials (Rubinstein et al 2010). In the analysis we will define response at the patient level (patients with significant inhibition of biomarkers), before analyzing the number of responding patients in the study sample.

Definition of response at the patient level:

Significant inhibition of biomarker activity is defined as the reduction in biomarker levels after four weeks treatment exposure (compared to baseline) that should satisfy two criteria: reduction is at least 50 % (biological), and reduction is sufficient when compared to the variation among the baseline values, to yield 95 % statistical confidence that it is not due to chance variations.

Variability will be measured on log-transformed values. The standard deviation (SD) will be the square root of baseline inter-patient variance. Pre- and post-treatment difference of log PIK1 values will be compared to the threshold of 1.6448 SD (normal distribution is used because number of samples is higher than 30), to establish statistically significant reduction at the one-sided 0.05 level.

Definition of a significant effect at study sample:

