Significant inhibition of biomarker activity will be declared if 5 of 36 patients have significant inhibition at patient level. Based on these assumptions, there is a 95% power to detect a true 35% rate of significant inhibition with an overall alpha error below 10%. As we consider three biomarkers in the primary analysis (cyclin D1, Ki67 and active caspase 3), the type I error was divided into 3,3% (<5%) for each analysis. Power and type I error has been derived from the binomial distribution (Rubinstein et al 2010), according to (A'Hern 2001).

Study dropouts

We assume the loss of patients between recruitment and end of study. Study dropouts will be analyzed as patients not displaying significant inhibition of the biomarker activity.

5.5 Randomization and blinding.

(ICH E3; 9.4.3, 9.4.6. ICH E9; 2.3.1, 2.3.2)

The randomization or blinding was not planned in this study.

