6 ANALYSIS SEQUENCE

6.1 Interim analysis

Prior to the completion of the study, an interim analysis with a cut-off dated 08-May-2018 will be performed in case the study was not completed up to that date. The results will be presented at the ASCO annual meeting 2018. The results will include patient characteristics in the different analysis populations. Primary and secondary biomarker analyses of the samples available up to that date and safety analyses.

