7.2 Populations for analysis

(ICH E3; 9.7.1, 11.4.2.5. ICH E9; 5.2)

Full analysis set

This set will include all the patients who have received the treatment. This set will also be the safety analysis set.

Per protocol set

This set will include all the patients of the full analysis set that do not have major protocol violations that may affect the assessment of treatment in the primary variable (e.g., non-evaluable patients for

biomarkers). The definition of these deviations is described in section 9.1. For the analysis of secondary variables, the number of evaluable patients for a certain biomarker analysis set will be considered.

Sensitivity analysis

The primary biomarker analysis (significant inhibition of cyclin D1, Ki67 and active caspase-3) and the secondary analyses will be performed in the full analysis set and the per protocol population.

The safety analyses will be performed in the full analysis set.

PKD population

We propose to analyze and model pharmacokinetics (PK), pharmacokinetics-pharmacodynamic (PBMC) and AZD2281 concentration, considering all patients with a complete treatment concentration-time profile.

Analyses will not be repeated between different analysis populations if they only differ by 10% patients. The largest analysis population will be used for the analyses.

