7.9 Interim analysis and data monitoring

(ICH E3; 9.7.1, 11.4.2.3. ICH E9; 4.1, FDA Feb 2010 "Guidance for Industry Adaptive Design Clinical Trials for Drugs and Biologics")

Prior to the completion of the study, an interim analysis with a cut-off date on 08-May-2018 will be performed in case the study was not completed up to that date. The results will be presented at the ASCO annual meeting 2018. The results will include patient characteristics in the different analysis populations. Primary and secondary biomarker analyses and safety analyses.

Alpha error correction methods for primary and secondary variables were described in the corresponding section.

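### SAP 5.4 and 7.8 give different rules for declaring significant inhibition (5 of 36 alone, or also a calendar-dated interim and both populations), and the stated power covers only the 5-of-36 rule

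*SAP*

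**What the plan says.** **The rule in SAP 5.4 (sample size).** "Significant inhibition of biomarker activity will be declared if 5 of 36 patients have significant inhibition at patient level". For this rule the section says "there is a 95% power to detect a true 35% rate of significant inhibition", with an overall alpha below 10% split as 3.3% for each of cyclin D1, Ki67 and active caspase 3. It derives both figures from the binomial distribution. No interim is mentioned. A patient counts as a responder when the biomarker falls by at least half and by more than 1.6448 baseline SDs on the log scale, the latter "to establish statistically significant reduction at the one-sided 0.05 level".

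**The rule in SAP 7.8 (multiplicity).** To correct alpha for multiple primary analyses, a biomarker difference can only be "declared when the analysis showed p-values <3.3% in the interim and the final analyses for both analysis populations", the populations being the full analysis set and the per-protocol set.

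**The interim in SAP 6.1 and 7.9.** It is fixed by date and is conditional: "an interim analysis with a cut-off dated 08-May-2018 will be performed in case the study was not completed up to that date". It uses the samples available by then and is meant for a congress presentation. Neither section gives it a size, a critical count, or any stopping or adaptation role. On alpha, 7.9 says only: "Alpha error correction methods for primary and secondary variables were described in the corresponding section".

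**Populations.** SAP 7.6 treats an analysis as positive only if the result agrees across all populations used. SAP 7.2 says: "Analyses will not be repeated between different analysis populations if they only differ by 10% patients". In that case the largest population is used.

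**The concern.** Sections 5.4 and 7.8 are both worded as the rule for declaring significance, and neither refers to the other. Suppose a biomarker ends with 5 or more responders among 36 but missed p<3.3% at the interim. Section 5.4 calls it positive and 7.8 does not. SAP 3.1 describes phase 0 studies as serving a go/no-go decision, so the reader needs to know which section decides.

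The strictness of the 7.8 rule also depends on how many patients happen to have paired tissue data on a calendar date. No document gives that number, and no power is stated for the combined rule. Nor does 7.8 say how its condition applies when no interim is held, or when 7.2 waives the per-protocol analysis.

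**Working it through.** **Inputs from the SAP.** n = 36 (5.4: "the sample size has been limited to 36 patients"); critical count 5; alternative rate 35%; alpha 3.3% per biomarker and below 10% overall (5.4, 7.8).

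**Assumptions.**
- The p-value in 7.8 comes from an exact one-sided binomial test on responder counts. The SAP does not name the test.
- The null rate is p0 = 5%. It is not stated; it is inferred from the one-sided 0.05 patient-level threshold in 5.4.
- One biomarker, one population, no dropout.
- The n1 interim patients are among the final 36. Because n1 is not stated, it is varied.

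**Step 1: the plan's own figures.**
- Alpha: P(Bin(36, 0.05) ≥ 5) = 0.0324, which is below 3.3%. Three times this is 0.0971, which is below 10%. Both alpha statements reproduce, which supports p0 = 5%.
- Power: P(Bin(36, 0.35) ≥ 5) = 0.9988. The stated 95% is met if read as a minimum, but it is not the exact power of this rule.

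**Step 2: the rule in 7.8, read as both looks required.** The interim critical count r1 is the smallest r with P(Bin(n1, 0.05) ≥ r) < 0.033. It is 2 for n1 = 2–6, 3 for 7–14, 4 for 15–24 and 5 for 25–35. Then

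P(declare) = Σ over k ≥ r1 of P(Bin(n1, p) = k) × P(Bin(36 − n1, p) ≥ 5 − k).

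| Interim n1 | r1 | Alpha per biomarker (p = 5%) | Power at 35% | Power at 25% |
|---|---|---|---|---|
| 12 | 3 | 0.75% | 84.9% | 60.7% |
| 18 | 4 | 0.72% | 92.2% | 69.3% |
| 20 | 4 | 1.00% | 95.6% | 77.3% |
| 24 | 4 | 1.69% | 98.7% | 88.1% |
| 30 | 5 | 1.56% | 99.3% | 90.2% |
| 35 | 5 | 2.90% | 99.8% | 95.9% |
| Final only | – | 3.24% | 99.9% | 96.6% |

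At 35%, power is below the stated 95% for every interim of 19 or fewer (94.1% at 19) and at least 95.5% for every interim of 20 to 35. The 25% column shows sensitivity only; the SAP claims power at 35% alone.

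**Step 3: how often the sections disagree.** Among trials positive under 5.4, the share refused by 7.8 is 1 − (joint power ÷ final-only power). At 35%:
- n1 = 12: 1 − 0.8486/0.9988 = 15.0%
- n1 = 18: 1 − 0.9217/0.9988 = 7.7%
- n1 = 20: 1 − 0.9555/0.9988 = 4.3%
- n1 = 24: 1 − 0.9866/0.9988 = 1.2%
- n1 = 30: 1 − 0.9925/0.9988 = 0.6%

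**Step 4: the other reading, a claim allowed at either look.** Alpha per biomarker is P(interim positive) + P(final positive) − P(both).
- n1 = 12: 0.0196 + 0.0324 − 0.0075 = 0.0444, or 13.3% over three biomarkers
- n1 = 18: 0.0109 + 0.0324 − 0.0072 = 0.0361, or 10.8%
- n1 = 24: 0.0298 + 0.0324 − 0.0169 = 0.0452, or 13.6%

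(Sums use unrounded terms.) The three-biomarker bound exceeds 10% for every n1 from 2 to 24. From 25 to 35 both critical counts are 5, so an interim success guarantees a final one and the bound stays at 9.7%.

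**The case against.** **The test in 7.8 may not be the responder test.** It speaks of biomarker differences and p-values, whereas 5.4 is a count threshold. SAP 7.1 assigns change in quantitative variables to the Wilcoxon test, and the planned Figure 2 is an inferential display of pre/post differences. If 7.8 means those tests, the figures above do not apply. This stands as a limit on the numbers. Against it, 7.8 opens with inhibition of the three biomarkers as the primary variable, and the binomial with p0 = 5% reproduces the stated alpha. The textual conflict needs none of these assumptions.

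**Section 7.8 may simply add a condition to 5.4.** Section 5.4 concerns sample size, 7.8 concerns multiplicity, and 7.9 points to the alpha section. That is a fair reading of intent. But 5.4 states its rule without qualification, and no power is given for the rule with the added conditions.

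**Power is not the basis of this design.** Section 5.4 sets 36 patients on clinical and practical grounds, and a sponsor may choose a strict rule. That is true, and it limits the weight of the power loss. It does not settle which rule applies.

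**Two stronger inferences are not supported.** A reader might infer that the interim look inflates type I error. As most naturally read, 7.8 requires both looks, and its error is below that of the final-only rule. Inflation arises only if the sentence means a claim at either look, and its stated purpose of correcting alpha argues against that. A reader might also infer that the trial is underpowered. The documents do not show this: the interim size is unknown, power at 35% stays at or above 95.5% with 20 or more interim patients, and nothing is lost if the study is complete by the cut-off.

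**Conclusion.** The concern holds as an inconsistency between 5.4 and 7.8 with unstated power; it should be corrected before analysis. The two sections can give opposite conclusions on the same final data, and the 95% power belongs only to the 5-of-36 rule.

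Under the stated assumptions, the final-only rule already satisfies the SAP's alpha limits, so the interim condition is unnecessary if claims are made only at the final analysis. Its cost at a 35% rate runs from about 15 percentage points of power with 12 interim patients (99.9% to 84.9%) to under one point with 30 (99.9% to 99.3%), and to nothing if no interim is held. Requiring the per-protocol set as well can only leave power equal or lower; that effect is not quantified here. Since the alternative reading would break the 10% limit for interims of 2 to 24, the wording needs settling whichever meaning was intended. Confidence in the textual conflict is high. Confidence in the size is moderate, because the test, p0 and the interim size are not given.

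**What to change.** 1. **In 7.8**, state that significance is declared only at the final analysis by the 5.4 rule: at least 5 of 36 in the full analysis set, exact binomial against p0 = 5%, 3.3% per biomarker. State that interim results are descriptive: responder counts with 95% confidence intervals and no significance claim.
2. **In the same edit, settle the populations.** Reconcile the both-populations condition in 7.8 and 7.6 with the 10% waiver in 7.2. Either keep the condition, taking the per-protocol critical count from the same test at the actual per-protocol n (5 for n = 25–36, 4 for 15–24) and saying what happens when the waiver applies, or make the per-protocol result a sensitivity analysis.
3. **In 5.4**, cross-refer to 7.8 and restate power for the rule kept: 99.9% at 35% for final-only in the full analysis set. If the both-looks rule is kept instead, write it into 5.4 with its power over the plausible interim sizes, and say how it applies if no interim is held.

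**Cost.** SAP wording only, with no added patients, samples or procedures. Protection is slightly less strict than under the both-looks rule (3.24% per biomarker against, for example, 0.72% with 18 interim patients) but stays within the stated 10%. No congress claim is lost, because the both-looks rule allowed none before the final analysis.

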7.9 Interim analysis and data monitoring

(ICH E3; 9.7.1, 11.4.2.3. ICH E9; 4.1, FDA Feb 2010 "Guidance for Industry Adaptive Design Clinical Trials for Drugs and Biologics")

Prior to the completion of the study, an interim analysis with a cut-off date on 08-May-2018 will be performed in case the study was not completed up to that date. The results will be presented at the ASCO annual meeting 2018. The results will include patient characteristics in the different analysis populations. Primary and secondary biomarker analyses and safety analyses.

Alpha error correction methods for primary and secondary variables were described in the corresponding section.

7.10 Statistical report conventions

7.10.1 Conventions to report data

All the tables, figures and lists will be presented in a vertical orientation, unless the horizontal orientation is required to view the information better. Legends will be used to describe the methods and results of these tables.

7.10.2 Statistical conventions

These tables will show the total patients in the sample of each analysis set or population in the headers of the columns (N=xxx). The total patients may also be presented in the table (n=xxx).

The summary of categorical variables will include the categories where the patients responded and the categories with missing values. All the summaries of continuous variables will include: N, mean and SD. Other summaries will be used (e.g., mean, quartiles, 5%, 95% intervals, CV or % CV), as appropriate. All percentages should be rounded up and only one decimal point should be reported (xx.x%). If percentages are reported as whole, percentages above 0% but <1% will be reported as <1%, whereas percentages above 99% but <100% will be reported as > 99%. A 100% percentage will be reported as 100%. 0% values should not be reported. Any percentage calculation resulting in 0% should be reported as a blank space. P-values will be reported with three decimal points after an initial zero value (0.001). p-values <0.001 will be reported as <0.001.

8 PROTOCOL DEVIATIONS

Description	Category	Does the deviation exclude the analysis population?			
		Full analysis and safety set	Per protocol set	Biomarker analysis subset	PKD population
Unsigned Informed Consent (main and sample).	Inclusion/Exclusion	Yes	Yes	Yes	Yes
Signed an outdated version.	Inclusion/Exclusion	Case by case	Case by case	Case by case	Case by case
The investigational product was not provided.	Treatment	Yes	Yes	Yes	Yes
Treatment was discontinued early, but the patient has received at least one administration.	Treatment.	No	Case by case	Case by case	Case by case
Patients with missing or non-evaluable pre-treatment and post-treatment biomarker/PK values.	Biomarker analysis	No	Case by case	Case by case	Yes
Patients who do not have type I primary endometrial carcinoma (EC) (see	Inclusion/Exclusion	No	Case by case	Case by case	Case by case

UICC-FIGO Classification [Stage]).						
Age < 18 years.		Inclusion/Exclusion	No	Case by case	No	No
ECOG>2.		Inclusion/Exclusion	No	No	No	No
Inappropriate organic function: ANC < 1.5 x 10 ⁹ /L Platelets < 100 x 10 ⁹ /L Hb ≤ 10g/dL Serum bilirubin > 1.5 x ULN INR ≥ 1.3 (o ≥ 3) ALT and AST > 2.5 x ULN Serum creatinine > 1.5 x mg/dL Serum cholesterol > 300 mg/dL or > 7.75 mmol/L Triglycerides > 2.5 x ULN		Inclusion/Exclusion	No	No	No	Case by case (PK-PD Modeling)
Prior anti-cancer treatments for current endometrial cancer.		Inclusion/Exclusion	No	Case by case	Case by case	Case by case
Major surgery or significant injury within the four weeks prior to start of the study drug.		Inclusion/Exclusion	No	Case by case	No	No
Side effects of any major surgery or major surgery throughout the study.		Inclusion/Exclusion	No	No	No	No
Serious and/or uncontrolled condition.		Inclusion/Exclusion	No	Case by case	Case by case	Case by case
Prior prohibited medication		Inclusion/Exclusion	No	Case by case	Case by case	Case by case
Pregnant or nursing (lactating) women.		Inclusion/Exclusion	No	No	No	No
Urine or serum pregnancy		Inclusion/Exclusion	No	No	No	No

test with positive result within 7 days before first dose administration.						
History of non-compliance with medical regimens.	Inclusion/Exclusion	No	Case by case	Case by case	Case by case	Case by case
Patients unwilling to or unable to comply with the protocol.	Inclusion/Exclusion	No	Case by case	Case by case	Case by case	Case by case
The study treatment was not administered according to the protocol: < 23 days or > 33 days	Treatment	No	Case by case	Case by case	Case by case	Case by case
The study treatment was not administered according to the protocol: dose > 600 mg/day	Treatment	No	Case by case	Case by case	Case by case	Case by case
The study treatment was not administered according to the protocol: Patients did not comply with the administration up to 3 days prior according to the protocol (>3 days for any reason).	Treatment	No	Case by case	Case by case	Case by case	Case by case
The study treatment was not administered according to the protocol: Patients did not comply with the minimum 50% (14 days) drug administration.	Treatment	No	Case by case	Case by case	Case by case	Case by case
The study treatment was not administered according to the protocol: Patients did not comply with the administration margin >6 days (3+3) for any reason.	Treatment	No	Case by case	Case by case	Case by case	Case by case
Toxicities not managed according to the protocol	Treatment Safety	No	Case by case	Case by case	Case by case	Case by case

(dose interruption/reduction, study treatment discontinuation/withdrawal not performed according to the protocol, toxicities not followed up 28 days post-treatment).						
The pre-treatment biopsy (MT1) was not collected.	Treatment	No	No	Case by case	No	
The pre-treatment biopsy (MT1) was not performed according to the protocol (biopsy date > 14 days prior to treatment start).	Biomarker analysis	No	Case by case	Case by case	Case by case	
The post-treatment surgery/biopsy was not performed according to the protocol (it was not performed +4 days upon end of treatment or any of the samples [MT2 paraffin/frozen, MNT2 frozen] was not collected).	Biomarker analysis	No	Case by case	Case by case	Case by case	
Pre-treatment blood sample was not collected according to the protocol (MS1 not collected or not collected before the first dose).	Biomarker analysis	No	Case by case	Case by case	Case by case	
Post-treatment blood sample in post-treatment was not collected according to the protocol (some of MS2 to MS7 samples were not collected, MS2 to MS6 samples were not collected 1-4 hours after	Biomarker analysis	No	Case by case	Case by case	Case by case	

the dose and/or MS7 sample was not collected 24 hours before the surgery).						
The patient was withdrawn from the study.	Safety	No	Case by case	Case by case	Case by case	Case by case
Serious concomitant diseases, including diseases that may interfere with drug absorption.	Safety	No	Case by case	Case by case	Case by case	Case by case
Visits performed outside of the window (Screening > 14 days, visits D7 to D28 > 7 ± 3 working days or follow-up visit > 35 days after the last dose).	Procedures	No	Case by case	Case by case	Case by case	Case by case
Screening assessments performed > 28 days prior to treatment start.	Procedures	No	Case by case	Case by case	Case by case	Case by case
D1 test performed > 3 days prior to treatment start date or not performed.	Procedures Safety	No	No	No	No	No
D7 to D28 tests, surgery and follow-up not performed one day prior or on the same day as the date of the visit or not performed.	Procedures Safety	No	No	No	No	No
Any test value not performed.	Procedures	No	No	No	Case by case (PK-PD Modeling)	Case by case (PK-PD Modeling)

